8.1.6.2 Clinical Laboratory Data

Clinical laboratory tests will be summarized at each visit. The baseline value will be the last non-missing measurement prior to the initial dose of study drug. Mean changes from baseline to each post-baseline visit, including Final Treatment Visit, will be summarized descriptively. Changes from baseline to maximum post-baseline CTCAE grade of laboratory values will also be summarized.

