Appendix C. Study Activities – Treatment Period

Activity	Screening	Day 1^a	Wk 4	Wk 8 (Arm B Only)	EOT (Arm A and Arm B) or Premature D/C from Treatment^b
Informed Consent ^c	X				
Dispense/Review Study Drug Dosing Card	X	X (Dispense only)	X	X	X (Review only)
Medical History ^d	X	X			
Physical Exam ^e	X	X			X
Vital Signs, Weight, Height ^f	X	X	X	X	X
ECG	X				
Hematology/Chemistry ^g /Coagulation Panel	X	X	X	X	X
Pregnancy Test (serum [s] urine [u]) ^h	X (s)	X (u)	X (u)	X (u)	X (u)
Anti-HCV Ab, Anti-HIV Ab	X				
Hepatitis B Panel	X				
HCV Genotype and Subgenotype	X				
FibroTest or FibroScan [®] or Liver Biopsy ^j	X				
Concomitant Medication Assessment	X	X	X	X	X
Adverse Event Assessment ^k	X	X	X	X	X
Study Drug Dispensed		X	X	X ^k	
HCV RNA Samples	X	X	X	X	X
Study Drug Accountability and Review of Study Drug Adherence			X	X	X ^l
HCV Resistance Sample		X	X	X	X

Activity	Screening	Day 1 ^a	Wk 4	Wk 8 (Arm B Only)	EOT (Arm A and Arm B) or Premature D/C from Treatment ^b
Pharmacokinetic Samples ^m			X	X	X
Child-Pugh Score (cirrhotic subjects only) ⁿ	X				X
Clinical Assessment of Hepatic Decompensation (cirrhotic subjects only) ⁿ		X			
HCC Screening Liver ultrasound (cirrhotic subjects only) ⁿ	X				
Patient Reported Outcomes Instruments (PROS) ^o		X			X
Flow cytometry sample ^p	X	X			X
HIV RNA ^p	X	X	X	X	X

Wk = Week; EOT = End of treatment; D/C = Discontinuation

* The EOT visit can be at Week 8 or 12 in accordance with treatment duration as described in Section 5.1.

- All procedures to be performed prior to first dose.
- Subjects who prematurely discontinue during the Treatment Period should return to the site to complete the Premature D/C Visit Procedures (preferably prior to the initiation of any other anti-HCV therapy).
- Subjects need to sign an IRB/IEC approved informed consent for the study (prior to performing any Screening or study-specific procedures).
- A complete medical history will be taken at Screening and will be updated at the Study Day 1 Visit.
- A symptom-directed physical examination may be performed at any other visit, when necessary. Any significant physical examination findings after the first dose will be recorded as adverse events.
- Height will be measured at the Screening Visit only.
- Blood samples for serum chemistry tests should be collected following a minimum 8-hour fast prior to study drug intake (with the exception of the Screening Visit, which may be non-fasting).

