Samples will be obtained at a minimum for the clinical laboratory tests outlined in [Table 5](#) at the visits indicated in [Appendix C](#) and [Appendix D](#).

Blood samples for serum chemistry tests should be collected following a minimum 8-hour fast prior to study drug intake (with the exception of the Screening Visit, which may be non-fasting). Subjects whose visits occur prior to the morning dose of study drug should

be instructed to fast after midnight until the blood sample is collected in the morning and thereafter take their study medications with food. Subjects whose visits occur following the morning dose of study drug should be instructed to fast after breakfast until the study visit occurs. At the Study Day 1 visit, a fasting blood sample should be collected prior to the first dose of study drug. Blood samples should still be drawn if the subject did not fast for at least 8 hours. Fasting or non-fasting status will be recorded in the source documents and on the laboratory requisition. The baseline laboratory test results for clinical assessment for a particular test will be defined as the last measurement prior to the initial dose of study drug.

A central laboratory will be utilized to process and provide results for the clinical laboratory tests.

Instructions regarding the collection, processing, and shipping of these samples will be provided by the central laboratory chosen for this study. The certified laboratory chosen for this study is Covance. Samples will be sent to the following addresses:

Covance
[name]
[name]

Table 5. Clinical Laboratory Tests

Hematology	Clinical Chemistry	Additional Tests
Hematocrit	Blood Urea Nitrogen (BUN)	Anti-HCV Ab ^a
Hemoglobin	Creatinine	HCV RNA
Red Blood Cell (RBC) count	Total bilirubin	HCV genotype and subtype ^a
White Blood Cell (WBC) count	Direct and indirect bilirubin	HIV Ab ^a
Neutrophils	Alanine transaminase (ALT)	HIV RNA ^b
Bands, if detected	Aspartate transaminase (AST)	Hepatitis B Panel (Anti-HB ^c
Lymphocytes	Alkaline phosphatase	Total, Anti-HBs and HBsAg) ^c
Monocytes	Sodium	Anti-HBc IgM ^c
Basophils	Potassium	Anti-HBc Total ^c
Eosinophils	Calcium	Anti-HBs ^c
Platelet count (estimate not acceptable)	Inorganic phosphorus	Anti-HAV
Prothrombin Time/INR ^a	Total protein	IgM ^d
Activated partial thromboplastin time (aPTT)	Glucose	Anti_HAV Total ^d
	Albumin	Anti-HEV IgG ^d
	Chloride	Anti-HEV IgM ^d
	Bicarbonate	HEV RNA ^d
	Magnesium	HBV DNA ^e

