11.3.1 Variables and Criteria Defining Abnormality

Hematology variables to be summarized include: hematocrit, hemoglobin, red blood cell (RBC) count, white blood cell (WBC) count, neutrophils, bands, lymphocytes, monocytes, basophils, eosinophils, platelet count, prothrombin time (PT), international normalized ratio (INR), and activated partial thromboplastin time (aPTT).

Chemistry variables to be summarized include: blood urea nitrogen (BUN), creatinine, total bilirubin, direct and indirect bilirubin, alanine aminotransferase (ALT), aspartate

aminotransferase (AST), alkaline phosphatase, sodium, potassium, calcium, inorganic phosphorus, total protein, glucose, albumin, chloride, bicarbonate, magnesium, gamma-glutamyl transferase (GGT), creatinine clearance (calculated using Cockcroft-Gault), and eGFR by MDRD.

The definitions of toxicity grades for laboratory parameters are presented in [Table 10](#).

Table 10. Definitions of Toxicity Grades 1, 2, 3, and 4 for Laboratory Values

Test	Grade 1	Grade 2	Grade 3	Grade 4
ALT	> ULN – 3 × ULN	> 3 – 5 × ULN	> 5 – 20 × ULN	> 20 × ULN
AST	> ULN – 3 × ULN	> 3 – 5 × ULN	> 5 – 20 × ULN	> 20 × ULN
Alkaline Phosphatase	> ULN – 2.5 × ULN	> 2.5 – 5 × ULN	> 5 – 20 × ULN	> 20 × ULN
Total Bilirubin	> ULN – 1.5 × ULN	> 1.5 – 3 × ULN	> 3 – 10 × ULN	> 10 × ULN
Hemoglobin	< LLN – 100 g/L	< 100 – 80 g/L	< 80 g/L	--
Absolute Neutrophil Count	< LLN – 1.5 × 10 ⁹ /L	< 1.5 – 1.0 × 10 ⁹ /L	< 1.0 – 0.5 × 10 ⁹ /L	< 0.5 × 10 ⁹ /L
Platelet count	< LLN – 75.0 × 10 ⁹ /L	< 75.0 – 50.0 × 10 ⁹ /L	< 50.0 – 25.0 × 10 ⁹ /L	< 25.0 × 10 ⁹ /L
INR	> 1 – 1.5 × ULN	> 1.5 – 2.5 × ULN	> 2.5 × ULN	--
Creatinine clearance	< LLN – 60 mL/min	< 60 – 30 mL/min	< 30 – 15 mL/min	< 15 mL/min
Albumin	< LLN – 30 g/L	< 30 – 20 g/L	< 20 g/L	--
White blood cells	< LLN – 3.0 × 10 ⁹ /L	< 3.0 – 2.0 × 10 ⁹ /L	< 2.0 – 1.0 × 10 ⁹ /L	< 1.0 × 10 ⁹ /L
Lymphocyte	< LLN – 0.8 × 10 ⁹ /L	< 0.8 – 0.5 × 10 ⁹ /L	< 0.5 – 0.2 × 10 ⁹ /L	< 0.2 × 10 ⁹ /L
GGT	> ULN – 2.5 × ULN	> 2.5 – 5 × ULN	> 5 – 20 × ULN	> 20 × ULN
Glucose (high)	> ULN – 8.9 mmol/L	> 8.9 – 13.9 mmol/L	> 13.9 – 27.8 mmol/L	> 27.8 mmol/L
Glucose (low)	< LLN – 3.0 mmol/L	< 3.0 – 2.2 mmol/L	< 2.2 – 1.7 mmol/L	< 1.7 mmol/L
Creatinine	> ULN – 1.5 × ULN	> 1.5 – 3 × ULN	> 3 – 6 × ULN	> 6 × ULN
Cholesterol	> ULN – 7.75 mmol/L	> 7.75 – 10.34 mmol/L	> 10.34 – 12.92 mmol/L	> 12.92 mmol/L
aPTT	> ULN – 1.5 × ULN	> 1.5 – 2.5 × ULN	> 2.5 × ULN	--
Sodium (low)	< LLN – 130 mmol/L	--	< 130 – 120 mmol/L	< 120 mmol/L

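### SAP Table 10 grades cholesterol, which is not a scheduled test, and omits calcium and inorganic phosphorus, which are, so neither analyte appears by grade in the laboratory toxicity outputs

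*Protocol*

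**What the plan says.** Protocol Table 5 (5.3.1.1, Clinical Laboratory Tests, Amendment 2) is the minimum list of tests: "Samples will be obtained at a minimum for the clinical laboratory tests outlined in" that table. Its chemistry column includes calcium and "Inorganic phosphorus", neither footnoted as screening-only. Cholesterol is in no column.

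SAP 11.3.1 names the chemistry variables to be summarized, among them "alkaline phosphatase, sodium, potassium, calcium" and, continuing the same list, inorganic "phosphorus, total protein, glucose, albumin, chloride, bicarbonate, magnesium". Cholesterol is not named there either.

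SAP Table 10, in the same section, sets limits for Grades 1 to 4. It has a cholesterol row, whose Grade 1 cell reads "> ULN – 7.75 mmol/L". It has no calcium or phosphorus row.

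Protocol 8.1.6.2 commits to a grade summary without restricting the analytes: "Changes from baseline to maximum post-baseline CTCAE grade of laboratory values will also be summarized". Protocol 6.1.7 names CTCAE Version 4 for grading laboratory abnormalities. SAP 12.1, which lists departures from the protocol, mentions only the removal of analyses for HIV co-infected subjects.

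**The concern.** A grade table should cover the parameters the study measures and intends to grade. This one covers an analyte outside the panel and leaves out two inside it, while grading the neighbouring electrolytes. Nothing in the SAP presents this as a choice.

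Safety is a primary objective (Protocol 4.1), and subjects at every CKD stage, including those on dialysis, may enroll (Protocol 5.2 and inclusion criterion 11). A reader of the report would expect the laboratory grade table to show any marked change in calcium or phosphate, and could take their absence to mean that none occurred.

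**Working it through.** No figure stated in the plan is at issue. The check compares three lists and then counts scheduled results.

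**The lists**

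| Parameter | Protocol Table 5 | SAP 11.3.1 | SAP Table 10 |
|---|---|---|---|
| Sodium, potassium, magnesium | yes | yes | graded |
| Calcium | yes | yes | no row |
| Inorganic phosphorus | yes | yes | no row |
| Cholesterol | no | no | graded |

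The Table 5 chemistry column has 18 entries, counting direct and indirect bilirubin as one. Eleven have a row in Table 10. The other 18 − 11 = 7 do not: BUN, direct/indirect bilirubin, calcium, inorganic phosphorus, total protein, chloride and bicarbonate.

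Table 10 has 24 rows for 20 distinct parameters. Two of the 20 are not in Table 5. Creatinine clearance is derived from creatinine and appears in SAP 11.3.1. Cholesterol appears in neither list, and is the only graded parameter of which that is true.

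**What follows from SAP 11.3.2**

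Grades are assigned only to parameters in the table it refers to. The maximum-grade tabulation, the count at grade 3 or higher and the trigger for the listing (an increase to grade 2 or higher) all use those grades. Calcium and phosphorus therefore enter none of the three. They remain in the change-from-baseline summaries and the low/normal/high shift tables.

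**Two further errors in the same place**

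- 11.3.2 refers to Table 11 for the graded laboratory parameters. Table 11 holds the vital-sign criteria; Table 10 is evidently meant.
- The potassium (low) row repeats the sodium (low) limits of 130 and 120 mmol/L. The potassium (high) row has its top grade above 7.0 mmol/L, so the two potassium rows cannot both be right.

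**Number of ungraded results**

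Inputs: the planned split of about 80 Arm A and 20 Arm B subjects (Protocol 5.1), and chemistry draws per Appendices C and D. Full attendance is assumed. Screening and Day 1 are excluded as baseline.

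- On treatment: Arm A has Week 4 and end of treatment; Arm B has Weeks 4 and 8 and end of treatment. 80 × 2 + 20 × 3 = 220.
- Post-Treatment Week 4: 80 + 20 = 100.
- Post-Treatment Week 12: 20 (Arm B only) under Appendix D footnote b. Footnote c says the panel is not required at that visit, and the note to SAP Table 3 gives chemistry only at Post-Treatment Week 4 or early discontinuation. So 0 to 20.

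Total per analyte: 220 + 100 = 320, or 320 + 20 = 340.

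**The case against.** The strongest reply is that Table 10 is a chosen subset. Seven chemistry entries lack a grade row, Protocol 8.1.6.2 does not say that every analyte will be graded, and the SAP exists to fill in such detail. The protocol's introduction also reports no blood chemistry findings of concern and no safety signal specific to CKD Stages 4 and 5. It is fair that a sponsor may grade a subset and that the documents show no particular calcium or phosphate risk. But the subset is not declared, and a table that grades an unscheduled analyte and repeats sodium limits for potassium does not look like one checked against this study's panel.

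Three stronger readings are tempting and not supported:

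- A reader might infer that cholesterol is never measured. Table 5 is a minimum list, and SAP 11.3 admits local results and extra testing prompted by a serious adverse event. Cholesterol is unscheduled, not excluded.
- A reader might infer that no severe calcium or phosphate change could be reported by grade anywhere. An abnormality reported as an adverse event would be graded and tabulated under SAP 11.2.2. That route is only partial: under Protocol 6.1.1.1 a laboratory abnormality counts as an adverse event only if it leads to discontinuation from the study, needs therapeutic intervention, or is judged one by the investigator. The shift tables are partial too, since a marginal and a marked change fall in the same category.
- A reader might take the count of results as a count of missed events. The planned tables count subjects by maximum grade, and the documents give no expected frequency of abnormal values.

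**Conclusion.** The mismatch stands in the current documents. Followed as written, the SAP produces no calcium or phosphorus grades in its laboratory toxicity table, grade 3 or higher count or grade 2 or higher listing trigger, which is an undeclared narrowing of Protocol 8.1.6.2.

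The size is 320 to 340 ungraded results per analyte on the planned enrollment and complete attendance. How many subjects would have reached a reportable grade is unknown, partly because the documents give no number of subjects with advanced CKD. The primary efficacy result is unaffected. This is a descriptive safety gap that should be closed.

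The finding assumes that Table 10 was read completely from the PDF. It runs without a break or redaction mark to magnesium (high), so a lost row is unlikely, but the original should be checked.

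**What to change.** In SAP Table 10, remove the cholesterol row and add rows for calcium (low and high) and inorganic phosphorus. Take the limits from CTCAE Version 4, the version named in Protocol 6.1.7; they are not reproduced in the protocol or SAP. Include both analytes in the maximum-grade table, the grade 3 or higher count and the grade 2 or higher listing.

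In the same edit, change the 11.3.2 references from Table 11 to Table 10, and correct the potassium (low) row against the same CTCAE version.

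If the sponsor prefers to leave any collected analyte ungraded, SAP 12.1 should say so.

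The cost is a table edit and a small amount of programming on data already collected. No new samples or visits are needed.

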5.3.1.2 Meals and Dietary Requirements

Study drug (GLE/PIB) tablets should be dosed together and taken with food.

5.3.2 Drug Concentration Measurements

5.3.2.1 Collection of Samples for Analysis

Blood samples for pharmacokinetic assay of GLE, PIB, and their possible metabolites will be collected by venipuncture at each study visit indicated below and in [Appendix C](#).

- At all Treatment-Period visits, except Day 1, a single blood sample for pharmacokinetic analysis will be collected without regard to the time of dosing. The date and time of blood sample collection and the two previous doses of the study drug will be recorded to the nearest minute in the source documents. Additionally, the date and time of the two previous doses of the study drug will be recorded to the nearest minute on the eCRF.

5.3.2.2 Handling/Processing of Samples

Specific instructions for collection of blood samples and subsequent preparation and storage of plasma samples for the pharmacokinetic assays of GLE, PIB, and their possible metabolites will be provided by the central laboratory, AbbVie, or its designee.

5.3.2.3 Disposition of Samples

The frozen plasma samples for the pharmacokinetic assays of GLE, PIB, and their possible metabolites will be packed in dry ice sufficient to last during transport, and transferred from the study site to the central laboratory.

The central laboratory will then ship the GLE and PIB samples to AbbVie or the reference laboratories following separately provided instructions.

5.3.2.4 Measurement Methods

Plasma concentrations of GLE and PIB will be determined using a validated assay methods in the Drug Analysis Department at AbbVie. Plasma concentrations of any possible GLE and PIB metabolites may also be determined using either validated or non-validated methods.

5.3.3 Efficacy Variables

Virologic response will be assessed by plasma HCV RNA levels in IU/mL at various time points from Day 1 through 12 weeks after completion or discontinuation of study drug.

5.3.3.1 Primary Variable

The primary efficacy variable is SVR₁₂ (HCV RNA < LLOQ 12 weeks after the last actual dose of study drug).

5.3.3.2 Secondary Variables

The secondary efficacy variables are:

- The percentage of subjects with HCV OTVF.
- The percentage of subjects with HCV virologic relapse.

5.3.3.3 HCV Resistance Variables

For all subjects receiving GLE/PIB and with available samples, baseline polymorphisms at signature resistance associated amino acid positions identified by next generation sequencing (NGS) and comparison to the appropriate prototypic reference sequence will be analyzed.

The following resistance information will be analyzed for subjects receiving study drug who do not achieve SVR₁₂ and who have a post-baseline sample with HCV RNA \geq 1000 IU/mL: 1) the amino acid substitutions in available post-baseline samples identified by NGS and comparison to the baseline sequence, 2) the amino acid substitutions in available post-baseline samples at signature resistance associated positions identified by NGS and comparison to the appropriate prototypic reference sequence, and 3) the persistence of resistance-associated substitutions by NGS.

5.3.4 Safety Variables

The following safety evaluations will be performed during the study: adverse events, vital signs, physical examination, ECG, and laboratory tests assessments.

5.3.5 Pharmacokinetic Variables

Individual plasma concentrations of GLE, PIB, and their potential metabolites, if measured, will be tabulated and summarized.

5.4 Removal of Subjects from Therapy or Assessment

5.4.1 Discontinuation of Individual Subjects

Each subject has the right to withdraw from the study at any time. In addition, the investigator may discontinue a subject from the study at any time if the investigator considers it necessary for any reason, including the occurrence of an adverse event or noncompliance with the protocol.

If, during the course of study drug administration, the subject prematurely discontinues, the procedures outlined for the applicable Premature D/C Visit should be completed as defined in [Appendix C](#) and [Appendix D](#). Ideally this should occur on the day of study drug discontinuation, but no later than 2 days after their final dose of study drug and prior to the initiation of any other anti-HCV therapy. However, these procedures should not interfere with the initiation of any new treatments or therapeutic modalities that the investigator feels are necessary to treat the subject's condition. Following discontinuation

of study drug, the subject will be treated in accordance with the investigator's best clinical judgment. The last dose of any study drug and reason for discontinuation will be recorded in the EDC (electronic data capture) system. The subject should then begin the Post-Treatment Period where the subject will be monitored for 12 weeks for HCV RNA and the emergence and persistence of resistant viral substitutions.

If a subject is discontinued from study drug or in the Post-Treatment Period with an ongoing adverse event or an unresolved laboratory result that is significantly outside of the reference range, the investigator will attempt to provide follow-up until a satisfactory clinical resolution of the laboratory result or adverse event is achieved.

In the event that a positive result is obtained on a pregnancy test for a subject or a subject reports becoming pregnant during the Treatment Period, the administration of study drug may be continued at the Principal Investigator's discretion after discussion with the subject, if the benefit of continuing study drug is felt to outweigh the potential risk. Specific instructions regarding subject pregnancy can be found in Section 6.1.6. If a subject is discontinued, subject will be monitored for SVR in the Post-Treatment Period as described in Section 5.1.3.

5.4.1.1 HCV Virologic Failure Criteria

The following criteria will be considered evidence of HCV virologic failure for the purposes of subject management:

- Confirmed increase from nadir in HCV RNA (defined as 2 consecutive HCV RNA measurement of $> 1 \log_{10}$ IU/mL above nadir) at any time point during study drug treatment.
- Confirmed HCV RNA ≥ 100 IU/mL (defined as 2 consecutive HCV RNA measurements ≥ 100 IU/mL) after HCV RNA $<$ LLOQ during study drug treatment.

When confirmatory testing is required, it should be completed as soon as possible and the subject should remain on study drug treatment until the virologic failure criteria has been

confirmed. Subjects meeting the virologic failure criteria will be discontinued from study drug and will continue to be followed in the Post-Treatment Period for the emergence and persistence of resistance-associated viral substitutions until 12 weeks post-treatment.

Alternative management will only be considered with the approval of TA MD.

5.4.1.2 Failure to Maintain HIV Virologic Suppression

HIV RNA will be assessed at each scheduled study visit during the Treatment and Post Treatment Period, as detailed in [Appendix C](#) and [Appendix D](#).

The criteria for failure to maintain HIV virologic suppression among subjects on stable ARTs is as follows:

- HIV RNA \geq 200 copies/mL confirmed on 2 consecutive tests at least 2 weeks apart, in a subject compliant with their HIV ARV therapy

Subjects should remain on HCV study drug treatment and his/her current ART regimen while the failure to maintain HIV virologic suppression is being confirmed. A confirmatory HIV RNA and HIV genotypic resistance blood draw can be done as an unscheduled visit. However, if this blood draw falls on the date of a scheduled study visit ([Appendix C](#) and [Appendix D](#)), only a single HIV RNA and HIV genotypic resistance blood draw needs to be performed at this visit.

At the time a confirmatory HIV RNA is drawn, a sample for HIV genotypic resistance testing should also be obtained; this sample will be analyzed if the subject's repeat plasma HIV RNA is \geq 500 copies/mL. Subjects should remain on HCV study drug treatment and his/her current ART regimen while the failure to maintain HIV virologic suppression is being confirmed. A confirmatory HIV RNA and HIV genotypic resistance blood draw can be done as an unscheduled visit. However, if this blood draw falls on the date of a scheduled study visit ([Appendix C](#) and [Appendix D](#)), only a single HIV RNA and HIV genotypic resistance blood draw needs to be performed at this visit.

During the Treatment Period, subjects with confirmed failure to maintain HIV RNA suppression should continue HCV study drug treatment unless there is a requirement for prohibited concomitant medications (Section [5.2.3.2](#)) to construct a new HIV ART regimen.

Clinical management of failure to maintain HIV virologic suppression during the study (Treatment and Post-Treatment Period) will be handled by the Investigator according to current HIV treatment guidelines and local standard of care. Subject's change of HIV ART regimen must be discussed with the AbbVie TA MD prior to the change being made, unless the change is being made to address an immediate safety concern.

